## 6. RESEARCH QUESTION AND OBJECTIVE(S)

### 6.1. Primary Objective

The overall objective of this global study is to describe participant characteristics and assess clinical outcomes and patient-reported outcomes among people with HIV who receive CAB+RPV LA regimen.

1. To describe baseline demographics, clinical characteristics and patterns of use among participants receiving CAB+RPV LA
  - Descriptive analysis of study population by baseline demographic and clinical characteristics
  - Monitor for use of OOLI
2. To assess the persistence, discontinuation, and adherence among participants receiving CAB+RPV LA
  - Persistence: Proportion of participants still on CAB+RPV LA at time of analysis, after 6, 12, and 24 months of use and at study end
  - Proportion of participants discontinuing the regimens of interest will be assessed
    - a. Reasons for discontinuation will be assessed

- Non-adherence to the dosing schedule will be assessed by:
  - a. Estimating the number of participants who missed 1 or more consecutive injections without taking daily oral bridging therapy or any other oral ARV regimen while not on CAB+RPV LA and estimating the mean and median number of injections missed during a 12-month period
  - b. Estimating the number of participants who received the injections more than 7 days earlier or later than their scheduled injection visit and median time from target injection to actual injection date of early delayed injections
  - c. Estimating the number of participants who missed 1 or more consecutive injections without taking daily oral bridging therapy or those who received the injections more than 7 days earlier or later than their scheduled injection visit (combined group A or B) and describe individual characteristics for the participants who are non-adherent.
  
- 3. To assess virologic effectiveness (i.e., proportion of participants experiencing virologic suppression and CVF) among participants receiving CAB+RPV LA regimen
  - Estimate overall number and proportion of participants with CVF and time to CVF (months)
  - Estimate the proportion of participants with CVF during the first 6 months after initiation of CAB+RPV LA
  - Estimate the proportion of participants with CVF 6, 12, and 24 months after initiation of CAB+RPV LA
  - Assessment of virologic suppression among participants on CAB+RPV LA regimen during first 6 months and at 6, 12, and 24 months after initiation of the regimen
  - Assessment of number and proportion of participants who remain suppressed (VL <50 c/mL) throughout all follow-up and at last follow-up
  
- 4. To assess factors associated with CVF among participants receiving CAB+RPV LA regimen

## 6.2. Secondary Objectives

1. Subgroup analyses by BMI (< 30, ≥ 30-<40 and ≥40 kg/m^2) at initiation, age at initiation (18-49, 50-64, ≥ 65 years), sex assigned at birth (female, male), race and ethnicity, sex/race, and country, if sample sizes allow, to assess characteristics, adherence, persistence, discontinuation, and virologic effectiveness
  
2. To estimate the frequency of documented injection site reactions and

hypersensitivity reactions among participants receiving CAB+RPV LA injections

3. To describe resistance and ART regimen among participants after discontinuation/CVF of CAB+RPV LA, where VL data are available and resistance testing has been done as part of routine clinical practice
  - Describe resistance (where this has been done as part of routine clinical practice) at the time of discontinuation/CVF and history of resistance and proviral DNA testing before discontinuation/CVF
  - Describe the ART regimen and virologic outcomes after discontinuation/CVF of CAB+RPV LA
    - To describe the demographic and clinical characteristics of participants who continue to stay on CAB+RPV LA as compared to those who switched regimens after discontinuation or CVF
    - To describe virologic response (suppression, non-response, CVF) to ART regimen after discontinuation/CVF of CAB+RPV LA
4. To describe reasons for initiating CAB+RPV LA, health-related quality of life, treatment satisfaction, treatment preference, treatment-related stigma, benefits, and reasons for missed injections and discontinuation among prospective participants (new initiators) of CAB+RPV LA
5. For data collected beyond the two-year follow-up period, outcomes will be analyzed at the extended time points

## 7. RESEARCH METHODS

### 7.1. Study Design

This is a non-interventional prospective observational cohort study using data from individual medical records, assessments from participating clinical sites, and participant-reported data from electronic questionnaires. Prospective participants will be followed from the date of their first CAB+RPV injection for a minimum of two years, unless they withdraw from the study, are lost to follow-up, or pass away. Participants that discontinue CAB+RPV LA and switch to a different ART regimen or to monthly CAB+RPV LA dosing schedule or experience CVF, will continue to be followed to describe virologic response and treatment switching. Retrospective participants will be included in the study regardless of whether they are still on CAB+RPV at the time of the study start and will have all applicable data collected. Participants who are deceased or lost to follow up will not be included.

For this non-interventional study, treatment and laboratory testing decisions will be made by the treating physician according to standard practice, taking into account the treatment history, individual characteristics, the approved prescribing information or summary of

[figure not shown]
product characteristics for CAB+RPV LA formulation, contemporary regimen and local guideline or recommendations. Testing for resistance and subtype at discontinuation/virologic failure will be part of the standard of care at selected sites, and the study will include only the clinical sites that conduct resistance and subtype testing as standard of care. The study protocol will be implemented by RTI Health Solutions (RTI-HS).

## 7.2. Study Population and Setting

The study population includes treatment-experienced, virologically suppressed (VL < 50 copies/mL) individuals who are 18 years or older and received at least one CAB+RPV LA injection with every-2 month dosing schedule, from participating clinical sites across several countries. Anticipated countries include the UK, Italy, Portugal, France, Spain, Germany, Japan, South Korea, Taiwan, Australia, Canada, and the US. Enrollment will take place as part of a participant’s standard of care visit at a participating site.

### Prospective Participants:

[figure not shown]
Prospective participants will include individuals enrolled from November 2025 until study size is reached. Participants will be enrolled prior to their first CAB+RPV LA injection, either during the optional oral lead-in (OOLI) phase, if applicable, or directly before their first CAB+RPV LA injection for those on the direct-to-injection (DTI) pathway. The baseline survey will be administered before the first CAB+RPV LA injection. The participants will be followed for a minimum of two years, unless they withdraw from the study, are lost to follow-up, or pass away. Participants who discontinue and switch to a subsequent regimen or who experience CVF will be followed-up for a minimum of 6 months and may be extended until viral load assessment is completed, with a maximum duration of 12 months.

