## STUDY INFORMATION

Title	CABFIDENCE: Global Real-World Evidence Cohort Study to evaluate Utilization, Clinical and Patient-Reported Outcomes among CAB+RPV LA users
Protocol version identifier	Amendment 1
Date of last version of protocol	01 May 2025
EU PAS (ENCEPP) register number	EUPAS1000000616
Active substance	Cabotegravir Rilpivirine
Medicinal product	VOCABRIA® 30 mg film-coated tablets Edurant® 25 mg film-coated tablets Cabenuva VOCABRIA® 400 mg/ 600 mg prolonged-release suspension for injection REKAMBYS® 600 mg / 900 mg prolonged-release suspension for injection
Product reference	NDA 212887 VOCABRIA (cabotegravir) tablets NDA 202022 EDURANT (rilpivirine) tablets NDA 212888 CABENUVA (cabotegravir extended-release injectable suspension; rilpivirine extended-release injectable suspension), copackaged, for intramuscular use
Procedure number	NA
Marketing authorisation holder(s)	ViiV Healthcare
Joint PASS	No

Research question and objectives	Using global real-world clinical data, this study will describe utilization, clinical and patient-reported outcomes among people with HIV on CAB+RPV LA regimen
Country(-ies) of study	Anticipated countries include United Kingdom, Italy, Portugal, France, Spain, Germany, Japan, South Korea, Taiwan, Australia, Canada, and the United States
Author	PPD [REDACTED] ViiV Healthcare PPD [REDACTED] PPD [REDACTED] ViiV Healthcare PPD [REDACTED]

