### 3. AMENDMENTS AND UPDATES

Amendment or update no	Date	Section of study protocol	Amendment or update	Reason
1	19 Oct 2025	Study objectives, study design, study population and setting, outcome definitions, confounders and effect modifiers, data sources, study size, data management, data analysis, ethics approval and subject consent and milestones	
Study design/study population and setting:
 
 
• Updated inclusion criteria for prospective participants (new initiators) that study enrollment should occur prior to the first CAB+RPV LA injection, either during the OOLI phase, if applicable, or directly before their first CAB+RPV LA injection for those on the DTI pathway
 
• Clarified the study design and population for retrospective and prospective participants
 
• Anticipated country scope revised to include Canada, Japan, South Korea, and Taiwan.
 
 
Data sources:
 
 
• Added that the baseline survey will be administered prior to the first CAB+RPV LA injection
 
 
Primary objectives:
 
 
• Updated adherence outcome definition to include both early as well as delayed injections.
 
• Added clarifying text to outcome definitions
 
	Protocol amended to reflect change in inclusion criteria for prospective participants to ensure baseline survey data is administered prior to first CAB+RPV LA injection, clarify study design and population for retrospective and prospective participants, to expand data collected to support primary and secondary objectives, to ensure clarity of outcome definitions, and to account for additional countries and increased estimated sample size

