**7.2.1 Inclusion criteria:**

- Diagnosis of HIV-1
- Aged  $\geq 18$  years at time of CAB+RPV LA injection
- Treatment experienced
- VL < 50 copies/mL at initiation
- Initiated every 2 month dosing CAB+RPV LA
  - For prospective participants, study enrollment should occur prior to the first CAB+RPV LA injection, either during the OOLI phase, if applicable, or directly before their first CAB+RPV LA injection for those on the DTI pathway
  - For retrospective participants, individuals who initiated CAB+RPV LA from January 2023 will be enrolled

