Emergent resistance	
 
▪ Proportion of participants with resistance and and proviral DNA testing at discontinuation/CVF.
 
		

Endpoint	Definition
	
 
▪ Proportion of participants with history of resistance and proviral DNA testing prior to discontinuation/CVF.
 
▪ The proportion of participants tested with any resistance mutation will be reported at discontinuation/CVF and history of prior to discontinuation/CVF, as will mutations associated with reduced susceptibility at the class-level and drug-level                             
 
○ All mutations will be reported; specific resistance mutations of interest to CAB+RPV LA can be highlighted and identified using the International Antiviral Society mutations list and Stanford HIV drug resistance database.
 
 
 

Patient-reported outcomes	
Reasons for initiating CAB+RPV LA	
 
▪ Descriptive summary of bespoke questionnaire (2 items) completed at baseline
 

Baseline adherence	
 
▪ Descriptive summary of bespoke questionnaire (7 items) completed at baseline
 

HIV health-related quality of life	
 
▪ Descriptive summary of WHOQOL-HIV BREF (31 items) completed at baseline, month 12 and discontinuation, if applicable
 

HIV treatment-related worries and stigma	
 
▪ Descriptive summary of HIV Treatment-Related Worries (HRW; 4 items) completed at baseline, month 12 and discontinuation, if applicable
 

Treatment-related benefits	
 
▪ Descriptive summary of bespoke questionnaire (7 items) completed at month 12, if applicable
 

Treatment satisfaction	
 
▪ Descriptive summary of HIVTSQs (12 items) completed at baseline and month 12, if applicable
 

Change in treatment satisfaction	
 
▪ Descriptive summary of HIVTSQc (12 items) completed at month 12, if applicable
 

Treatment preference	
 
▪ Descriptive summary of bespoke questionnaire (3 items) completed at month 12, if applicable
 

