#### 7.4. Data Sources

- **Participant surveys:** Prospective participants of CAB+RPV LA will be asked to complete an online survey at enrollment, at month 12 (if applicable), and if they discontinue CAB+RPV LA. The baseline survey will be administered prior to the first CAB+RPV LA injection. The online survey will include the WHOQOL-HIV BREF, the HIVTSQs, and the HIVTSQc (O’Connell, 2012; Woodcock and Bradley, 2001; Woodcock and Bradley, 2006) and several bespoke questionnaires developed for this study. Appropriate agreements with the copyright owners will be in place for use in this study. It is estimated that the participant surveys will take approximately 20 minutes to complete.
- **Participant medical information via site-completed eCRF:** The investigator or authorized medical staff will record clinical and treatment data from participants’ medical records into an eCRF at enrollment, minimum of two annual follow-ups (unless participant discontinued CAB+RPV LA) and at study end.

Participant surveys and medical record information will be linked by a common participant identifier (ID) code that will be retained by the site.

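### The baseline survey is tied to the first injection, so for oral lead-in users it falls during the lead-in, and one baseline for satisfaction and treatment worries covers two treatment states

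*Protocol*

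**What the plan says.** Section 7.2 (Prospective Participants) sets the enrolment window by pathway. For oral lead-in (OOLI) users: "Participants will be enrolled prior to their first CAB+RPV LA injection, either during the optional oral lead-in (OOLI) phase, if applicable". For the others, enrolment is "directly before their first CAB+RPV LA injection for those on the direct-to-injection (DTI) pathway". The inclusion criteria in 7.2.1, the synopsis and the study-size paragraph of the synopsis follow the same rule.

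The survey is attached to enrolment. Under Section 7.4, prospective participants are "asked to complete an online survey at enrollment, at month 12 (if applicable), and if they discontinue CAB+RPV LA". The one timing limit is in 7.2: "The baseline survey will be administered before the first CAB+RPV LA injection". Section 3 gives the reason for the amended enrolment rule: "to ensure baseline survey data is administered prior to first CAB+RPV LA injection".

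Section 7.3.2 defines the satisfaction outcome as "Descriptive summary of HIVTSQs (12 items) completed at baseline and month 12, if applicable". The treatment-related worries items and the WHOQOL-HIV BREF are listed at baseline, month 12 and discontinuation. Seven bespoke adherence items are listed at baseline only. HIVTSQc is listed at month 12 only. Section 7.7.2 plans descriptive summaries of items and scores on observed data. Section 6.1 provides for monitoring OOLI use.

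**The concern.** A rating of satisfaction with treatment, or of worries about it, depends on which treatment the respondent is taking. A direct-to-injection (DTI) participant has not yet had any study drug when surveyed. Eligibility requires treatment experience and viral suppression, so the natural reading is that this person rates the regimen being left. An OOLI participant surveyed during the lead-in has already begun the transition. The design text does not spell out what the lead-in consists of, but the Study Information table lists "VOCABRIA® 30 mg film-coated tablets Edurant® 25 mg film-coated tablets" among the medicinal products, so oral cabotegravir plus rilpivirine is a sound inference.

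At stake is the interpretation of secondary objective 4. HIVTSQs and the worries items are collected at baseline and again at month 12, which invites the reader to compare the two. For DTI participants that comparison runs from the earlier regimen to the injections. For OOLI participants it runs from the lead-in tablets to the injections, which is a different question. The amendment was meant to protect the baseline, but it anchored the survey to the injection and not to the start of the regimen.

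**Working it through.** **Timing, by pathway**

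| | OOLI | DTI |
|---|---|---|
| Enrolment (7.2, 7.2.1) | during the lead-in | directly before first injection |
| Survey (7.4) | at enrolment | at enrolment |
| Limit on survey (7.2, 7.4) | before first injection | before first injection |
| State when answering | lead-in under way | no lead-in, no injection yet |
| Label in 7.3.2 | baseline | baseline |

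The protocol does not ask for a survey before the lead-in, does not tell OOLI participants which regimen to answer about, and does not separate survey results by pathway.

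**By instrument**

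- HIVTSQs and treatment-related worries concern treatment by name and definition, so the mixed state bears on them directly.
- The WHOQOL-HIV BREF is listed as health-related quality of life, not as a rating of a regimen.
- The wording and recall period of the bespoke adherence items are not shown. They may ask about earlier therapy. Their reference regimen is undefined.

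**Size**

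The plan has no figure of its own on this point. Table 1 concerns the precision of a proportion and is not an input. The only usable input is 1,750 expected new initiators (7.5). The OOLI share f and the score shift s (mean on lead-in minus mean on the prior regimen, in SD units, sign unknown) are not given, so what follows is illustration.

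Pooled baseline mean = (1 − f) × prior mean + f × (prior mean + s) = prior mean + f × s.

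Standard error of the pooled mean, if all 1,750 answer: 1/√1,750 = 0.0239 SD.

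With s assumed to be 0.2 SD:

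| f (assumed) | OOLI participants | f × s (SD) | divided by 0.0239 |
|---|---|---|---|
| 5% | 88 | 0.01 | 0.4 |
| 10% | 175 | 0.02 | 0.8 |
| 25% | 438 | 0.05 | 2.1 |
| 50% | 875 | 0.10 | 4.2 |
| 75% | 1,312 | 0.15 | 6.3 |

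The shift equals one standard error at f = 0.0239/s. That is about 12% for s = 0.2 (0.0239/0.2 = 0.12), about 24% for s = 0.1 and about 5% for s = 0.5. Within the OOLI group the full shift s applies whatever f is. A pooled comparison of month 12 with baseline moves by −f × s.

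**The case against.** The strongest reply is that nothing the protocol plans is broken. Objective 4 is to describe. Each instrument gets a descriptive summary, no change-from-baseline score is stated, and HIVTSQc is completed at month 12 and not computed from the baseline survey. The protocol never says that baseline must describe the prior regimen. The index date is the first injection, so a survey before the injection agrees with the study's own time zero. Splitting tables by pathway is ordinary material for a statistical analysis plan, which is not shown, and Section 7.7.1.1 allows stratification by other clinical variables.

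Much of this stands, and it rules out four stronger readings:

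- That a planned change score is biased. None is planned. The point is limited to whatever comparison of baseline with month 12 is made.
- That no baseline instrument describes the prior regimen. Item wording and recall periods are not in the document.
- That subgroup or country results on patient-reported outcomes are made non-comparable. Sections 6.2 and 7.7.1.1 name the subgroup outcomes, and patient-reported outcomes are not among them.
- That a known number of participants have a wrong baseline. The OOLI share is not given.

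It is also fair that enrolment during the lead-in does not settle whether a survey at the visit that starts the lead-in comes before the first tablet. In some cases it may, but the protocol neither requires this nor records it.

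The appeal to a later analysis plan does not remove the core. Survey timing is a rule of data collection. An analysis plan can separate OOLI from DTI participants, but it cannot recover answers about the prior regimen that were never collected, and Section 4 starts data collection in November 2025. Agreement with the index date suits the clinical outcomes. It does not tell the reader which treatment a satisfaction score refers to.

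**Conclusion.** The point holds in limited form. For OOLI participants the protocol's baseline is before the injection but not necessarily before the regimen, so one baseline for HIVTSQs and treatment-related worries mixes two treatment states. Any comparison with month 12 carries that mix. For the WHOQOL-HIV BREF and the adherence items, the finding is only that the reference regimen is unstated.

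The size is unknown. Under an assumed shift of 0.2 SD and full survey completion, the effect on the pooled mean is below sampling error at an OOLI share of 5% or 10% and above it from about 12%. The conclusion also rests on reading the lead-in as oral cabotegravir plus rilpivirine, which the product list implies. Only a secondary, descriptive objective is touched; the primary outcomes and Table 1 are not affected. It should be corrected early, because each survey taken under the present rule fixes that participant's baseline for good.

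**What to change.** In Sections 7.2 and 7.4, with the matching line in the synopsis, have the baseline survey completed before the first oral lead-in tablet when the participant is approached in time, and before the first injection for DTI participants. Anyone first approached during the lead-in should still be enrolled and followed. Their survey record should show that it was taken on lead-in, and their baseline and month 12 results for the treatment-specific measures should be summarised separately from those of participants surveyed on their prior regimen. It would also help to state which regimen the bespoke adherence items refer to.

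The cost is a sentence or two on timing, one field at survey and one split in the tables, and OOLI use is already monitored. The downside is that somewhat fewer participants will have a baseline on the prior regimen where sites reach people only once the lead-in has begun. Treatment and clinical follow-up do not change.

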**Retrospective Participants:**

Retrospective participants will include individuals who initiated CAB+RPV LA from January 2023 and will be followed for up to two years. Participants who have discontinued CAB+RPV LA for any reason will be included and participants who are deceased or lost to follow up will not be included. Participants who discontinue and switch to a subsequent regimen or who experience CVF will be followed-up for a minimum of 6 months and may be extended until viral load assessment is completed, with a maximum duration of 12 months.

The sampling methodology will be designed with the goal of maximising the probability that each individual treated with CAB+RPV LA will have an equal opportunity to be selected. Participants will be enrolled as they come in for a scheduled visit, however if the volume of participants at a site is large, a customized, site-specific sampling approach may be devised to achieve an efficient method of obtaining a representative sample of participants. In some sites, it is likely that all treated participants will be selected.

The study will aim to select a diverse group of medical practices to represent diversity in clinical practice settings and to support recruitment of a diverse sample of participants (e.g., prioritizing non-cisgender males, individuals aged 50 years or older, and individuals with BMI  $\geq 30$  kg/m^2).

Individuals who are viremic (VL  $\geq 50$  copies/mL) at initiation will not be included in this study. Individuals with VL results available around the time of initiation at VL  $< 50$  copies/mL will be included in the study regardless of VL levels following enrollment.

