#### **4. MILESTONES**

Milestone	Planned/Estimated date
Draft Protocol	7 March 2025
Registered with HMA-EMA catalogue	30 April 2025
Final Protocol	01 May 2025
Protocol Amendment	19 October 2025
Start of data collection	November 2025
First Interim Tables (Data through December 2025)	
 
Preliminary Version - December 2025
 
Final Version – April 2026
 

Second Interim Tables (Data through October 2026)	
 
Preliminary Version - December 2026
 
Final Version – April 2027
 

Third Interim Tables (Data through October 2027)	
 
Preliminary Version - December 2027
 
Final Version – April 2028
 

Final report (Data through when follow-up is completed on all participants)	
 
Preliminary Version - –6 months after end of data collection
 
Final Version – 12 months after end of data collection
 

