**7.3.2. Outcome Definitions**

Endpoint	Definition
Primary	
Persistence	
 
▪ Proportion of participants still on CAB+RPV LA at time of analysis, after 6, 12, and 24 months of use and at study end
 

Discontinuation	
 
▪ Proportion discontinuing after last injection:                             
 
○ Date of discontinuation will be the date of the last injection prior to:                                     
 
▪ no injections and no documentation of oral bridging for more than 127 days after any injection.
 
 
 
 
 

Endpoint	Definition																	
	
 
▪ Physician confirmed treatment switch from CAB+RPV LA to another ARV regimen
 
▪ Physician confirmed treatment stop of CAB+RPV LA
 
▪ Median time to discontinuation
 
▪ Proportion of participants who discontinued and reinitiated the regimen within 6 months from discontinuation
 
																	

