## **8. PROTECTION OF HUMAN SUBJECTS**

### **8.1. Ethical Approval and Subject Consent**

The study will be conducted in accordance with legal and regulatory requirements; with scientific purpose, value, and rigor; and will follow generally accepted research practices described in GPP issued by Public Policy Committee of the ISPE.

Ethics review requirements and processes for prospective studies vary among countries and are governed by local standards. This study will be conducted in accordance with such standards in each country.

RTI-HS, with assistance from local clinical research associates, will work in collaboration with the site Principal Investigators to submit the necessary ethics review applications in each country at both the site and the national or regional levels, as well as notify/register the local Health Authority, as and where applicable.

Informed consent will be obtained from participants (or their legally acceptable representative) by site study staff before data collection. The person obtaining consent will be responsible for ensuring that each participant fully understands the nature, purpose, risks, and benefits associated with participation. Each participants will be provided with a copy of his or her signed informed consent form. The investigator, or a person designated by the investigator, will retain the original of each participant's signed consent form.

Participants (or the participant's legally acceptable representative) may choose to withdraw consent at any time. At time of withdrawal, all data that have already been processed and analyzed will be kept to guarantee the integrity of the study. Once data has been processed and analyzed (i.e., at the point of data analysis), the information may continue to used.

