**11. PLANS FOR DISSEMINATING AND COMMUNICATING STUDY RESULTS**

The target audience for these data includes healthcare providers, health plan population-based decision-makers, and regulatory and health authorities.

Abstracts will be prepared for both the interim and final analysis, with a manuscript developed from the final data set. All publications will comply with the *International Committee of Medical Journal Editors (ICMJE)* guidelines. A final full study report will be submitted to the Sponsor. Study results will be submitted to scientific conferences and for peer-reviewed journal publication.

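### Retrospective participants enter only if alive, not lost and attending a visit, which biases their persistence upward; 12-month results at interims 1–2 and 24-month results at interims 1–3 rest on them alone

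*Protocol*

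**What the plan says.** - **Retrospective entry.** Protocol 7.2 (Retrospective Participants) takes people who initiated from January 2023 and follows them for up to two years. It includes those who have stopped the regimen but adds that "participants who are deceased or lost to follow up will not be included". Section 7.1 and the Synopsis repeat the exclusion. On recruitment, 7.2 says "Participants will be enrolled as they come in for a scheduled visit". Section 8.1 requires consent first: "Informed consent will be obtained from participants (or their legally acceptable representative) by site study staff before data collection".
- **Prospective entry.** Enrolment runs from November 2025 and takes place before the first injection. Death or loss ends follow-up but does not remove the participant.
- **Outcome.** Under 7.3.2, one trigger for discontinuation is "no injections and no documentation of oral bridging for more than 127 days after any injection".
- **Analysis.** Section 7.7.1.1 counts person-time from the first injection and mentions no delayed entry. Enrolment type is not among its listed strata. Section 7.7.1.3 plans no sensitivity analyses, and 7.9 does not mention this selection.
- **Size.** Section 7.5 expects 250 retrospective and 1,750 prospective participants. It describes the 250 as already on the regimen, which does not sit well with the inclusion of people who have stopped.
- **Interims.** Section 4 sets data cuts at December 2025, October 2026 and October 2027. Section 11 adds: "Abstracts will be prepared for both the interim and final analysis".

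**The concern.** The same event is handled in opposite ways. A prospective patient who stops attending passes 127 days without an injection or documented bridging and counts as discontinued. A retrospective patient with the same history leaves both numerator and denominator, because the entry rule never admits them. Time between first injection and enrolment is therefore immortal with respect to death and loss. For anyone who started before November 2023, that is the whole two-year window.

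Recruitment at scheduled visits may add to this, since people coming every two months for injections may be met more often than those who have stopped. That would work against the aim in 7.2 of giving every treated person an equal chance of selection. The protocol gives no visit frequency for people off the regimen, so I put no figure on it.

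At stake is primary objective 2 (persistence and discontinuation), above all at the interim time points that no prospective participant can yet have reached. An analysis plan cannot recover people who were never enrolled.

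**Working it through.** **1. The plan's own precision.** Clopper-Pearson limits reproduce all 40 widths in Table 1 to within 0.0001. For N = 2,000 the widths are 1.28% at a 2% rate and 2.13% at 6%, as 7.5 states. For N = 1,750 they are 1.37% and 2.28%.

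**2. Longest possible prospective follow-up** (from 1 November 2025 to the last day of each cut in section 4):

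| Cut | Days | Months | 12 months reached? | 24 months reached? |
|---|---|---|---|---|
| December 2025 | 60 | 1.97 | no | no |
| October 2026 | 364 | 11.96 | no | no |
| October 2027 | 729 | 23.95 | yes | no |

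So 12-month results at interims 1–2 and 24-month results at interims 1–3 are retrospective only. So are 6-month results at interim 1. The 12-month result at interim 3 is not: anyone starting from November 2025 to October 2026 can contribute. The protocol text gives no assessment window; a window around the time point would admit only the earliest enrolments.

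**3. Bias in retrospective discontinuation.** Let D be the true discontinuation proportion and q the share of it that occurs through death or loss. The protocol gives neither, so both are assumptions. Removing those people gives an observed proportion of D(1 − q)/(1 − Dq).

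- D = 20%, q = 25%: 0.15/0.95 = 15.8%, bias 4.2 points.
- D = 20%, q = 50%: 0.10/0.90 = 11.1%, bias 8.9 points.
- D = 10%, q = 25% to 50%: 7.7% to 5.3%, bias 2.3 to 4.7 points. This also serves as a 12-month case if discontinuation by then is 10%.
- D = 30%, q = 25% to 50%: 24.3% to 17.6%, bias 5.7 to 12.4 points.

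The overall range is 2.3 to 12.4 points. Persistence rises by the same amount.

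**4. Set against sampling error.** At 80% persistence the exact 95% interval is 74.5% to 84.8% for n = 250 (half-width about 5 points) and 78.2% to 81.7% for n = 2,000 (about 1.8 points). In a pooled final estimate the retrospective weight is 250/2,000 = 12.5%, so a bias of 4.2 to 8.9 points becomes 0.125 × 4.2 = 0.5 to 0.125 × 8.9 = 1.1 points.

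**5. CVF.** Let c be the true proportion (4% assumed), L the excluded share, and k the ratio of recorded CVF risk in excluded to included people. The observed value is c/((1 − L) + kL).

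- k = 1: no bias.
- k = 2, L = 5%: 0.04/1.05 = 3.8%. k = 5, L = 15%: 0.04/1.60 = 2.5%.
- k = 0 (lost people yield no later viral loads, hence no recorded event): 0.04/0.95 = 4.2% at L = 5%, and 0.04/0.85 = 4.7% at L = 15%.

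The sign depends on k, which the protocol does not give.

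**The case against.** The strongest reply is that the protocol limits the selection and that the final result barely moves. Most of this stands, and it rules out several stronger readings a reader might infer.

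- **That the retrospective group contains only current users.** It does not. People who stopped for any reason but remain in care are included, so selection is on death, loss to care and visit attendance. Section 7.2 also allows site-specific sampling aimed at a representative sample and expects some sites to take everyone treated. Neither brings back the deceased or lost.
- **That every 12- and 24-month interim result rests on this group.** The 12-month result at interim 3 does not.
- **That CVF is biased downward.** This needs a higher recorded CVF risk among those excluded, which nothing in the protocol establishes. CVF requires a measured viral load, so the bias could run either way.
- **That the protocol orders pooling.** No sentence does. Pooling is implied by objectives written for participants as a whole and by the precision statement for 2,000. Section 7.5 also shows precision for each group, and an analysis plan that is not shown may separate them.
- **That the bias clearly exceeds sampling error at the interims.** The half-width of 5 points assumes all 250 are enrolled and evaluable. The evaluable number may be smaller and the interval wider.

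The formula also counts every death or loss as a discontinuation. The protocol does not classify a death within 127 days of the last injection, and it mentions estimators that allow for right-censoring. If some of these people would have been censored, the bias is smaller. Finally, section 11 plans interim abstracts without saying which time points they will report.

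**Conclusion.** The point holds in this limited form. The entry rule biases persistence upward and discontinuation downward in the retrospective group, because a lost patient who would meet the 127-day rule is never enrolled. No direction can be claimed for CVF.

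On assumed inputs (20% true 24-month discontinuation, 25–50% of it through death or loss) the retrospective bias is about 4–9 points, or 2.3–12.4 points if discontinuation is 10–30%. At 12 months it is about 2–5 points if discontinuation by then is 10%. In the final pooled estimate it is about 0.5–1.1 points, within the half-width of about 1.8 points, so the final report is not seriously distorted.

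The main exposure is at the interim time points that are retrospective only, where bias and sampling error may be of similar size and nothing in the protocol requires a label. This is a cheap improvement to a descriptive study, not a flaw that undermines it.

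**What to change.** 1. In 7.7.1.1, report persistence, discontinuation, adherence, suppression and CVF by enrolment type, with the roughly 1,750 prospective participants as the headline set. Cost by Table 1: the CI widens by 0.09 points at a 2% rate (1.28% to 1.37%) and by 0.15 points at 6% (2.13% to 2.28%).
2. Show the retrospective group separately, labelled as conditional on being alive and in care at enrolment.
3. For any pooled rate or time-to-event estimate, use delayed entry at enrolment. Retrospective participants whose two years ended, or who stopped the regimen, before enrolment then add nothing to a pooled discontinuation estimate and appear only in the separate table.
4. Label 12-month results at interims 1–2 and 24-month results at interims 1–3, and any abstract using them, as retrospective only. The same label fits 6-month results at interim 1. The tables need not be emptied.
5. Add this selection to the limitations in 7.9.
6. Where sites can supply it, collect an aggregate count of initiators since January 2023 who were deceased, lost or not enrolled. This replaces the assumed loss share with a figure and lets the bias be bounded.

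Items 1–5 need wording and table layout only; item 6 needs one count per site.
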